- To describe the prevalence of common radiological bowel signs in patients with confirmed AMI vs. suspected but eventually non-confirmed diagnosis of AMI
- To describe the prevalence of common radiological bowel signs in patients with different subtypes of AMI (arterial occlusive, venous, NOMI, other/unclear).

Study questions

- 1) What is the frequency rate of common radiological bowel signs (Table 1) among AMI patients with and without salvageable bowel?
- 2) Is it possible to distinguish the AMI patients with and without salvageable bowel with the use of a CT-based AMI score composed of common radiological signs?
- 3) Is it possible to differentiate the patients with and without AMI with the use of CT-based AMI score composed from common radiological signs?

Hypothesis

It is possible to differentiate between AMI patients with salvageable and non-salvageable ischemic bowel damage using the score based on CT radiological bowel signs.

Study outcomes

Primary study outcomes: Frequency rate of common radiological signs in AMI patients with and without salvageable bowel. Radiological score value in AMI patients according to the stage of bowel ischaemic damage.

Secondary study outcomes:

Frequency rate of common radiological signs/findings among patients with confirmed and suspected but eventually not confirmed AMI.

Performance of the radiological score in patients with different types of AMI.

Methods

This is a substudy of the AMESI study - "Incidence, Diagnosis, Management, and Outcome of Acute Mesenteric Ischaemia: A Prospective, Multicentre Observational Study." As of the end of August 2023, a total of 705 patients from 32 study sites worldwide have been enrolled, with 418 of them having confirmed cases of AMI. For patients with confirmed AMI, comprehensive data collection concerning diagnostics, management, and long-term outcomes has been completed (refer to Appendix 1).

Patients:

From the final AMESI cohort, we will select 6-7 sites limited to Europe due to logistical reasons related to the installation of software for the transmission of full CT investigations in impersonalized form. We expect to obtain images of at least 100 patients with confirmed AMI. Only study sites with more than 20 patients in total enrolled in the study will be asked to contribute radiological data. The CT scans will be gathered through AMESI's dedicated international online platform, and a retrospective visual and

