The AMESI database of pseudonymized CT-s can be accessed via an online platform with the personal identification of selected and authorized study group members. For participants in the AMESI study, the consent to use the clinical and imaging data has been obtained or waived at enrolment, based on local ethics rules. A centralized collection of radiological images was planned in the study protocol of the AMESI study. Installation of software for pseudonymizing CT images will require additional institutional approval from each site.

Data collection:

Patients' clinical and demographic characteristics, including baseline data, AMI event data, management data, histology data, and hospital outcome data will be retrieved from the RedCap database of the AMESI study (Appendix 2), or from the Tartu University Hospital patient data management system.

Data Retention:

The data collected during the study will be stored securely on Tartu University servers till 31.12.2039 and will be securely removed after this date. Only authorised study team members will have access to the data.

Allocation of patients into study groups:

To test the hypothesis, the study patients will be divided into the following study groups:

	Control Cases	Patients with confirmed AMI. Target: 100 - 200	
		AMI patients with salvageable bowel	AMI patients with non-salvageable bowel
No of pt	Target: 50-100	Target: 50-100	Target: 50-100

Definition of the patient group	Patients included in the AMESI study as suspected AMI	Patients included in the AMESI study with confirmed AMI, who did not undergo bowel resection Patients with one of the following:	Patients included in the AMESI study with confirmed AMI who (one of the following): 
 1) treated endovascularly and did not undergo bowel resection secondarily 2) received surgical revascularization without bowel resection (initial or secondary) 3) received explorative laparoscopy or laparotomy without the need for bowel resection (initially or secondarily) 4) received conservative treatment without the need for secondary bowel resection
---------------------------------	---	--	---

Radiological Methods:

CT scans with intravenous contrast media relevant to the hospitalization of selected patients from the AMESI study cohort will be pseudonymized and uploaded to the online AMESI database. The selection of CT scans will be based on the initial diagnostic hypothesis of acute abdomen or suspicion of AMI.

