Inclusion Criteria: CT scan of the entire abdominal cavity / full body using intravenous contrast media.

Exclusion criteria: Scans without the use of an intravenous contrast media or those covering only a partial area of the abdomen will be excluded.

Two radiologists, who will be blinded to the original radiology report, clinical diagnosis and outcome of the patient, will review the CT scans. The CT images will be screened for radiological signs indicative of mesenteric ischaemia (Table 1). The presence of these signs will be recorded as indicated in the Table. In order to develop a radiological score, the bowel signs are used.

Statistics

Obtaining radiological data:

Interobserver agreement for CT findings will be determined with the κ statistic and classified as follows: $\kappa = 0\text{--}0.2$, slight agreement; $\kappa = 0.21\text{--}0.4$, fair agreement; $\kappa = 0.41\text{--}0.6$, moderate agreement; $\kappa = 0.61\text{--}0.8$, substantial agreement; and $\kappa = 0.81\text{--}1$, almost perfect agreement.

Disagreements between the two reviewers will be resolved by consensus. Consensual data will then be used for final statistics.

Descriptive statistics:

We will compare epidemiological data and CT signs between patients with and without salvageable bowel damage. Pearson Chi-square or Fisher tests will be used for the comparison of categorical variables, and the Student t-test or Wilcoxon rank-sum test for the comparison of continuous variables as appropriate. A frequency table for the occurrence of radiological symptoms in study groups will be constructed.

Workout of radiological CT-score

In order to develop a radiological score, the bowel signs are used (Table 1, 3-7). We will compare CT signs

- 1) between the patients with salvageable and non-salvageable bowel damage;
- 2) between the patients with confirmed and suspected but eventually not confirmed AMI. The conceptual approach is presented in Figure 1.

[figure not shown]

Figure 1. Conceptual approach for radiological score.

Pearson Chi-square or Fisher tests will be used for the comparison of categorical variables, and Student t-test or Wilcoxon rank-sum test for the comparison of continuous variables as appropriate.

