2.	Occlusion of superior mesenteric vein/or branches	No contrast enhancement on MDCT scan in porto-venous phase/lack of contrast enhancement within the vessel lumen / The thrombosed superior mesenteric vein is seen as a large, distended vessel that does not fill appropriately with contrast / a low-attenuation filling defect on contrast-enhanced CT.
Bowel signs:		
3.	Bowel dilatation	
Abnormal dilatation of small or large bowel loops compared to the adjacent normal bowel loops. Evaluation of 3 different bowel segments is carried out – small bowel, large bowel and caecum.
 
Abnormal dilatation is considered if the diameter is:
 
- >30 mm for small bowel- >60 mm for large bowel- >90 mm for caecum 
Documentation of the findings:
 
1. No bowel dilatation2. Unsure/uncertain/technically difficult to evaluate3. Bowel dilatation present by radiologist assessment, specify the bowel segment

		
4. Maximum bowel diameter in mm in three locations: small bowel, caecum large bowel, caecum
 
Classification of the findings on bowel diameter will be worked out through the analysis of the results. First, cut-off values of bowel dilatation for prognostication of unsalvageable bowel for each segment under review will be identified. Second, Their weights will be identified and incorporated into the score.

4.	Decreased, absent or abnormal bowel wall enhancement	
No contrast enhancement, segmental enhancement decrease of bowel loops in comparison with adjacent normally enhancing bowel loops or abnormal hyperenhancement of bowel loops.
 
Documentation of the findings:
 
 1. Normal bowel wall enhancement 2. Unsure/uncertain finding/technically difficult to evaluate 3. Hyperenhancement of the bowel wall 4. Decreased/diminished enhancement 5. No enhancement in the venous phase 
Evaluation of bowel wall enhancement will be documented in two different ways:
 
 1. Small bowel, large bowel and caecum wall density is measured and documented in Hounsfield units (HU) 2. Visual evaluation of 4 quadrants of the abdomen and identifying visual differences of segmental bowel wall enhancement in comparison to adjacent bowel loops. If a difference is identified the segmental HU values are measured in visually normal and altered bowel loops. The significant difference is analysed further statistically.

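### Absolute bowel-wall HU is recorded with no contrast phase fixed, so comparing it between patients mixes scan phase with ischaemia; scans without a venous series also lack a defined code for absent enhancement

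*Protocol*

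**What the plan says.** Under Radiological Methods, the inclusion criterion is a "CT scan of the entire abdominal cavity / full body using intravenous contrast media". The exclusion is equally broad: "Scans without the use of an intravenous contrast media or those covering only a partial area of the abdomen will be excluded". Neither mentions phase, so an arterial-only scan of the whole abdomen qualifies. Two clinical indications are accepted: "The selection of CT scans will be based on the initial diagnostic hypothesis of acute abdomen or suspicion of AMI". Under Patients, the protocol states "we will select 6-7 sites limited to Europe due to logistical reasons"; no common acquisition protocol is described.

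Table 1, sign 4 (bowel wall enhancement) is documented in two ways.

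- The first is absolute: "Small bowel, large bowel and caecum wall density is measured and documented in Hounsfield units (HU"). No phase is named.
- The second is a visual reading against adjacent loops, after which "If a difference is identified the segmental HU values are measured in visually normal and altered bowel loops". Again no phase is named.

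The visual codes run from 1 to 5. Code 5 is "No enhancement in the venous phase"; codes 1 to 4 name no phase. Code 2 is "Unsure/uncertain finding/technically difficult to evaluate".

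Under Statistics, continuous variables are compared between groups with a t-test or rank-sum test. Findings with a univariate p-value of 0.1 or less enter a multivariate model, and each score weight comes from a univariate logistic model with the sign as the only independent variable.

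**The concern.** The HU value of an enhancing bowel wall depends on when after injection the image is taken. Table 1 itself treats phase as part of a sign's definition: the arterial-occlusion sign names the arterial or venous phase, the venous-occlusion sign the porto-venous phase, and code 5 of sign 4 the venous phase. The absolute HU measurement is the exception. Where a patient has both series, the two readers are not told which to measure. Where a patient has only one, the value is pooled with values from other phases.

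Two things are at stake. First, a real difference in wall HU between salvageable and non-salvageable bowel is diluted, or a difference appears that reflects acquisition. Secondly, the visual category depends on which series exist: non-enhancing bowel is code 5 when a venous series is available, but may become code 4 or code 2 when it is not. Phase is not listed for recording, so a later analysis could not correct for it without returning to the images.

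**Working it through.** The protocol gives no HU figure and no phase distribution, so there is no stated number to reproduce. The calculation below shows scale only.

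**From the protocol:** 50-100 patients per group (Allocation of patients into study groups); entry threshold p ≤ 0.1 (Workout of radiological CT-score).

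**Assumed:** within-phase SD 20 HU; arterial-only scans shift wall HU by g, taken here as a lowering; arterial-only shares pA and pB in the two groups; true ischaemia effect d of 20 HU (lower in group A) or 0.

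**1. AUC of pooled HU.** For one pair of patients in given phases, the chance of correct ordering is Φ(Δ / (20√2)) = Φ(Δ / 28.28), where Δ is d plus the phase shift between the two. The pooled AUC averages this over the phase combinations.

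- Single phase, d = 20: Φ(20/28.28) = 0.76.
- Equal shares of 40%, g = 30, d = 20: both in the same phase, weight 0.36 + 0.16 = 0.52, Δ = 20; only A arterial, weight 0.24, Δ = 50; only B arterial, weight 0.24, Δ = -10. AUC = 0.52 × 0.760 + 0.24 × 0.961 + 0.24 × 0.362 = 0.71.
- Equal shares of 20%, g = 15, d = 20: 0.75. Over shares of 20-40% and g of 15-30, the range is 0.71-0.75.
- No ischaemia effect: AUC = 0.5 + (pA - pB)(Φ(g/28.28) - 0.5), where Φ(15/28.28) = 0.702 and Φ(30/28.28) = 0.856. With 50% versus 20%: 0.5 + 0.3 × 0.202 = 0.56 and 0.5 + 0.3 × 0.356 = 0.61. Reversed: 0.44 and 0.39.
- Milder imbalance, 30% versus 20%, no effect: 0.52-0.54; reversed, 0.46-0.48.
- True AUC 0.76 with a 50/20 imbalance in either direction: 0.62 to 0.80.

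**2. Passing the p ≤ 0.1 screen with no ischaemia effect.** Spurious difference = g(pB - pA). Variance in each group = 20² + g²p(1 - p). Standard error = √((vA + vB)/n). Two-sided normal test, shares 20% versus 40%:

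| g (HU) | Spurious difference (HU) | Chance, 50 per group | Chance, 100 per group |
|---|---|---|---|
| 10 | 2 | 14% | 18% |
| 20 | 4 | 24% | 36% |
| 40 | 8 | 44% | 68% |

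With one fixed phase the chance is 10%. A larger sample makes the false signal more likely to pass.

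**3. Noise alone.** With equal shares of 30%, the SD becomes √(400 + 0.21g²), that is 20.5, 22.0 or 27.1 for g = 10, 20 or 40. At 50 per group, power for a true 10 HU difference at p ≤ 0.1 falls from 80% to 79%, 74% or 58%.

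**The case against.** The case on the other side has real force on several points.

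- **The second way of measuring sign 4 is within-patient.** Normal and altered loops are compared in the same person. If both are read in one series, phase is shared and largely cancels as a between-patient confounder, although the size of the contrast may still depend on phase. A reader might infer that all HU comparisons are compromised; the protocol does not support that.
- **Code 5 names its phase.** It would be wrong to say that it ignores phase. What remains is that no code is stated for a scan without a venous series. Code 2 could absorb such scans, but is not said to.
- **The comparison with unconfirmed cases is not shown to be worse.** One might argue that suspicion drives the scan protocol, so confirmed versus suspected AMI is most exposed. But the controls were themselves enrolled as suspected AMI, and come through the same centres. No document-based reason makes either comparison the more vulnerable.
- **The HU analysis is not spelled out.** The t and rank-sum tests are assigned to continuous variables in general, and AUC is planned for the score, not for HU alone. The AUCs above are therefore a scale for the problem, not a forecast of a planned result, and no effect on the five-sign score has been shown.
- **Some handling may sit elsewhere.** Phase adjustment or a venous-only sensitivity analysis could be left to an SAP, and the appendix describing the retrieved clinical data is not shown.

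The last point does not dispose of the matter. The phase in which HU is measured is part of the sign's definition, and Table 1 is where this protocol defines signs. A covariate that was not recorded cannot be adjusted for later without going back to the scans.

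**Conclusion.** The point holds for absolute wall HU compared between patients: the stated eligibility and measurement rules allow values from different phases to be pooled, and no stated analysis step separates them. If phase mixes are equal across groups the cost is noise (AUC 0.76 reading 0.71-0.75 under the assumptions). If they differ there is bias (an uninformative measure reading 0.56-0.61 at 50% versus 20%, but only 0.52-0.54 at 30% versus 20%). The SD, phase shift and shares are all assumed. A reader might infer that bias has been demonstrated; it has not, because the protocol gives no phase distribution. The separate, smaller fault is the missing code for absent enhancement when no venous series exists. This should be corrected, but it affects one of five bowel signs and does not undermine the study as a whole.

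**What to change.** Before reading starts:

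1. Record for each scan which contrast phase or phases are available.
2. State in Table 1 that absolute wall HU is measured in the portal-venous series where one exists. Otherwise analyse it stratified by or adjusted for phase, or normalised to a reference in the same series.
3. Require the normal and altered loops in the second measurement to be read in the same series.
4. Where there is no venous series, code absence of enhancement as 'not assessable: no venous series', separate from code 2.
5. Repeat the sign 4 analysis in venous-phase scans only.

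The cost is one extra field per scan and fewer scans in the venous-only analysis. The protocol's data-integrity checks cover slice counts and the presence of required DICOM tags, but do not say that phase is among them. The field should therefore be planned as a reader entry, not assumed to come from the metadata.

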CT with contrast media enhancement has become the most accurate technique for diagnosing AMI, with a reported specificity between 90 and 100% [3,4], and is considered the first-line imaging modality when AMI is suspected. In addition to recognition of AMI, CT imaging has the potential to differentiate between reversible and irreversible ischaemic intestinal damage [5, 6]. **This is a pivotal moment in choosing the treatment strategy** – in the absence of irreversible damage; reperfusion therapy can restore intestinal viability and thus avoid bowel resection.

Various radiological signs are routinely used to detect bowel ischaemia in CT imaging. The list includes vascular – occlusion of mesenteric arteries or veins – and bowel signs – bowel dilatation, decreased or absent bowel wall enhancement, pneumatosis intestinalis, gas in the mesenteric or portal veins, and bowel wall thinning (Table 1). The capability of these signs to describe the stage of ischaemia has been addressed in some studies. A recent meta-analysis demonstrated that bowel wall thinning, decreased or absent bowel wall enhancement, bowel dilation, pneumatosis intestinalis, porto-mesenteric venous gas, and mesenteric artery occlusion are independent risk factors predicting transmural necrosis (5), whereas decreased or absent bowel wall enhancement and bowel dilation were predictive for

transmural necrosis also in venous occlusive AMI. The same meta-analysis showed that bowel wall thickening and increased bowel wall enhancement were not predictive of transmural necrosis (5). Importantly, while the specificity of these radiological findings, when considered individually, is considerably high—up to 98%—the sensitivity remains very low, ranging from 30% to 40% (5).

Based on this, we hypothesize that **combining multiple signs may enhance the diagnostic performance of CT scanning in distinguishing various stages of ischemic bowel damage.**

From a practical perspective, it is important to predict who **requires bowel resection** and who has **potentially salvageable bowel**. Bowel resection is a disabling surgery that significantly affects a patient's quality of life. Whenever possible, it should be avoided. If the bowel is salvageable, an endovascular procedure can restore mesenteric blood supply – this allows avoiding laparotomy and is considerably less traumatic for the patient.

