The present study will elucidate whether the presence of five common radiological bowel signs on CT, either alone or in combination, may distinguish between no bowel ischaemia (suspected AMI) vs. reversible (AMI treated without bowel resection) vs. irreversible ischaemic damage (AMI treated with bowel resection).

To accomplish this, CT scans from patients enrolled in the multicentre international study (The AMESI study, Clinical Trials: NCT05218863) will be collected and subjected to retrospective analysis by the investigating radiologists. After analysing predefined radiological signs separately for their association with the need for bowel resection, the feasibility of combining different CT findings will be explored with the goal of **establishing a practical CT-based radiological scoring system for separating patients with reversible and irreversible bowel ischaemic damage.**

As different subtypes (arterial, venous, and non-occlusive mesenteric ischemia) have different pathoanatomical courses, differences in radiological bowel signs may be expected. To overcome this variability, we will first elaborate the score based on all patients with a confirmed diagnosis of AMI. As a second stage, we will test the score by including only patients with arterial occlusive AMI. If these two created scores appear to be different, we will test them mutually and in subgroups of other subtypes of AMI. The ultimate goal is to have one radiological score identifying the magnitude of bowel damage that could be used for any form of AMI, with possible minimized adaptations needed subtypes.

Considering the low number of venous AMI and NOMI we will primarily not create separate scores for these subtypes. If the performance of created scores appears insufficient in our study, these subtypes need to be assessed in a separate study.

Objectives

The primary objective of the study is to **create a CT-based AMI score using radiological signs that would enable the differentiation between patients with salvageable and non-salvageable ischemic bowel damage.**

The specific objectives are as follows:

- To describe the prevalence of common radiological bowel signs (Table) in AMI patients with and without irreversible ischaemic damage of the bowel.
- To assess the prognostic capability of these radiological bowel signs, both individually and in combination, for predicting irreversible ischaemic damage of the bowel.

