All CT findings with a univariate p -value ≤ 0.1 were entered into a multivariate logistic regression model to gauge their independent association with non-salvageable bowel damage (comparison 1) or confirmed diagnosis of AMI (comparison 2). The radiological score will be constructed based on univariate logistic regression models, where the dependent variable will be non-salvageable bowel and the independent variable will be radiological sign. The number of models will be equal to the number of radiological signs. The coefficient from the model will be uprounded and used as a weight for the radiological sign. In case the weights from the univariate models are clinically not relevant, expert opinions will be used instead. All the radiological signs will then be multiplied with the assigned weights and then summed. Finally, one by one the radiological signs will be left out of the score to test, whether a simpler version of the score would also give as good results as the more complicated version. The goodness of the score will be evaluated using AUC. A similar score will be constructed for suspected vs confirmed AMI.

However, if this will not result in a useful score, we will use a more complicated approach based on interactions between the radiological signs and interpretations of the results from the simpler approach.

In the first approach, **two scores** will be constructed.

- 1) using data of all patients with confirmed AMI
- 2) using data of only patients with confirmed arterial occlusive AMI

The performance of these two score will be tested in the following cohorts:

- a) all patients with confirmed AMI
- b) only occlusive arterial AMI included
- c) only non-occlusive AMI included
- d) Patients with venous occlusive AMI excluded
- e) Patients subjected to palliative care excluded

Table 1. Common radiological signs used to detect bowel ischaemia in CT imaging

	Radiological sign	Description
Vascular signs:		
1.	Occlusion of superior/inferior mesenteric artery/or its respective branches	No contrast enhancement on MDCT scan in the arterial phase or in the venous phase/lack of contrast enhancement within the vessel lumen / Acute arterial thrombi and emboli may appear as obvious low-attenuation filling defects in the SMA, its branches, or other major mesenteric arteries.

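### Screening the CT signs at univariate p ≤ 0.1 before the multivariable model biases the reported adjusted odds ratios of weak and moderate signs, although the five bowel signs are already pre-specified; the score itself is not affected.

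*Protocol*

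**What the plan says.** In the Protocol, Statistics, under Workout of radiological CT-score, the rule is that the CT findings with a univariate p-value of at most 0.1 "were entered into a multivariate logistic regression model to gauge their independent association with non-salvageable bowel damage". The outcome is non-salvageable bowel in comparison 1 and confirmed AMI in comparison 2. The univariate p-values come from the tests named just before: "Pearson Chi-square or Fisher tests will be used for the comparison of categorical variables", with a t-test or Wilcoxon test for continuous measures.

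The candidate signs are fixed in advance: "In order to develop a radiological score, the bowel signs are used (Table 1, 3-7"). These are dilatation, wall enhancement, pneumatosis, mesenteric or portal venous gas, and wall thickness.

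The score is built separately. Each sign gets its own univariate logistic model, the rounded coefficient becomes its weight, and signs are then left out one at a time and judged by AUC. No p-value filter is stated for that route.

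Among the specific objectives is this one: "To assess the prognostic capability of these radiological bowel signs, both individually and in combination".

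**The concern.** A sign passes the screen only if its observed difference is large enough. For a weak or moderate sign, the samples that pass tend to be those in which chance exaggerated the difference. Fitting the adjusted model to the same patients carries that exaggeration into the odds ratios, while a real sign that missed the threshold gets no adjusted estimate at all.

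A screen is usually defended as a way to cut a long candidate list. Here the list has five pre-specified items. The screened model is also the only one in the simpler approach that adjusts the signs for one another, so a reader who wants to know what one sign adds given the others would rely on it.

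**Working it through.** **Inputs from the protocol**
- Threshold p ≤ 0.10; two-sided is assumed, as sidedness is not stated.
- Group sizes: the allocation table targets 50–100 salvageable and 50–100 non-salvageable. The Patients subsection says "We expect to obtain images of at least 100 patients with confirmed AMI", which is 50 per group if split evenly.
- The only effect figures are in the Background: per-sign sensitivity of 30–40% and specificity of up to 98%. The second figure is a maximum; no lower bound is given. The sign rate in salvageable bowel may thus be as low as 2%, with no stated upper limit.

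The protocol gives no expected odds ratio or power, so there is no figure of its own to reproduce. All rates in salvageable bowel below are assumptions and are shown as a range.

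**Step 1: chance of failing the screen.** For binary signs and n per group, with p̄ = (p₁ + p₂)/2,

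power = Φ{ [ (p₁ − p₂) − 1.645·√(2p̄(1 − p̄)/n) ] / √[ (p₁(1 − p₁) + p₂(1 − p₂))/n ] }, and drop rate = 1 − power.

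Example, 30% vs 15%, n = 50:
- p̄ = 0.225, and the pooled SE is √(2 × 0.225 × 0.775/50) = 0.0835.
- The unpooled SE is √((0.21 + 0.1275)/50) = 0.0822.
- Power = Φ((0.15 − 1.645 × 0.0835)/0.0822) = Φ(0.15) = 0.56, so the drop rate is 44%.

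Exact enumeration of both binomials gives 43% with Pearson chi-square and 54% with Fisher.

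**Step 2: the range.** The table uses exact enumeration with Pearson chi-square. Inflation is the geometric mean odds ratio (0.5 added to each cell) among samples that pass, divided by that among all samples.

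| Rates (non-salvageable vs salvageable) | True OR | Dropped, n = 50 | Inflation if kept, n = 50 | Dropped, n = 100 |
|---|---|---|---|---|
| 30% vs 2% | 21 | 0.3% | ×1.01 | 0% |
| 30% vs 5% | 8.1 | 3% | ×1.04 | 0% |
| 30% vs 10% | 3.9 | 18% | ×1.18 | 2% |
| 30% vs 15% | 2.4 | 43% | ×1.41 | 18% |
| 40% vs 25% | 2.0 | 50% | ×1.41 | 26% |
| 30% vs 20% | 1.7 | 68% | ×1.68 | 50% |

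Fisher's test drops more in the moderate and weak rows: 25%, 54%, 59% and 77% in the last four rows at n = 50.

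**Step 3: the multivariable model itself.** Five binary signs, each at 30% vs 15%, were simulated with 50 per group and a latent correlation of 0 or 0.3.

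| Latent correlation | Large-sample adjusted OR | All five entered (median) | Screened, among kept signs |
|---|---|---|---|
| 0 | 2.4 | about 2.6 | about 3.5 |
| 0.3 | 1.7 | about 1.8 | about 2.5 |

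All five real signs survived the screen together in only 6–11% of samples. At 35% vs 5%, about 1% of signs were dropped and there was no material inflation.

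**Step 4: is there room for all five?** With one term per sign, 50/5 = 10 to 100/5 = 20 events per term. If dilatation is split into three segments and enhancement into four non-reference categories, the count is 3 + 4 + 1 + 1 + 1 = 10 terms, or 5–10 events per term.

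**The case against.** The strongest reply is that the protocol's own literature figures point to strong signs. It says that specificity "is considerably high—up to 98%—the sensitivity remains very low, ranging from 30% to 40% (5"). At 30–40% vs 2%, under 1% of real signs are dropped at 50 per group and inflation is at most 1.01. That stands for signs of that kind. It does not cover every sign:
- 98% is the upper end.
- The Background reports wall thickening and increased enhancement as not predictive, yet Table 1 includes hyperenhancement in item 4 and thickening in item 7.
- The cited specificity is for transmural necrosis, while this study groups patients by resection. If 20% of the unresected group had necrosis (an assumption), a sign with 30% sensitivity and 90% specificity would appear in 0.2 × 30% + 0.8 × 10% = 14% of that group, for an odds ratio of about 2.6.

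The second reply is that nothing important depends on this model. That is largely right. Three further inferences are also not supported:
- **That screened-out signs are treated as having no effect.** They are still weighted and summed in the score and still appear in the frequency table.
- **That an adjusted odds ratio is a stated objective.** The objective speaks of capability alone and in combination, which the univariate models and the score's AUC also serve. Leaving signs out one at a time is another check on what each adds.
- **That the confidence intervals are too narrow.** In the moderate-effect settings checked, coverage of 95% intervals stayed near 94–96%. What is shown is a shift in the estimates.

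The third reply, that Table 1 codes more than five terms, is correct and limits the 10–20 events per term to one term per sign.

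**Conclusion.** The point holds as a limited defect in how the adjusted associations are estimated, and it is worth correcting because correction is cheap. For moderate and weak signs at 50 per group, the screen removes real predictors in 18–68% of studies and inflates the kept univariate odds ratios by about 1.2 to 1.7 times. For highly specific signs the effect is negligible, and at 100 per group it is much smaller.

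A reader might conclude that real predictors are lost about half the time at 50 per group. The documents do not support that as a general statement: it needs a true odds ratio of about 2.0–2.2, which the protocol does not give, and it uses the low end of the 50–100 target.

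The bias is confined to the adjusted odds ratios reported for comparisons 1 and 2; the score as written does not draw on the screened model. The sizes assume equal groups, binary signs and a two-sided test. They were computed for comparison 1 only, and measures in mm or Hounsfield units would have different power.

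**What to change.** Replace the p ≤ 0.1 entry rule with a statement that all five bowel signs (Table 1, items 3–7) enter the multivariable model without univariate screening, each as one pre-defined term. Use a Firth or similar penalty, since rare and highly specific signs may separate. Report all five odds ratios with confidence intervals, for both comparisons. The univariate comparisons can stay as description.

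No new data are needed. The wording change is short, but it requires deciding beforehand how each sign's multi-level or multi-segment coding in Table 1 reduces to a single term. Intervals become slightly wider. If segments or categories are kept as separate terms, events per term fall below 10–20, which is a further reason for the penalty.
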